#### **3.2 Exclusion Criteria**

Refer to Participant Eligibility Checklist in Appendix A.

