### **4.1 Informed Consent Forms and Screening Logs**

Written informed consent for participation in the study must be obtained before performing any study-related procedures. Informed Consent Forms for enrolled patients and for patients who are not subsequently enrolled will be maintained at the study site.

All screening evaluations must be completed and reviewed to confirm that patients meet all eligibility criteria before enrollment. The investigator will maintain a screening log to record details of all patients screened and to confirm eligibility or record reasons for

screening failure, as applicable.

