## 9. STUDY CALENDAR

	Screening a	Treatment Cycles (21-day cycles)					Surgery	Follow-Up (or Treatment Discontinuation b )
		Cycle 1		Cycle 2		Cycle 3		
	Within 28 days prior to start of treatment	Day 1 (± 3 days)	Day 14 (± 7 days)	Day 21 (± 3 days)	Day 38 (± 4 days)	Day 42 (± 3 days)	2-4 weeks after Cycle 3	10 days ± 5 days after surgery (or < 30 days after last treatment)
Informed consent	X c							
Baseline tumor tissue sample d	X							
Second tumor tissue sample, if clinically feasible			X					
Demographic data	X							
Medical history and baseline conditions	X							
Vital signs e	X	X		X		X		X
Weight	X	X		X		X		X
Height	X							
Complete physical examination f	X							X
Limited physical examination g		X		X		X		
Digital Photography	X		X				X	
ECOG Performance Status	X							X
ECG h	X							
Hematology i	X j	X k		X		X		X

	Screening a	Treatment Cycles (21-day cycles)					Surgery	Follow-Up (or Treatment Discontinuation b )
		Cycle 1		Cycle 2		Cycle 3		
	Within 28 days prior to start of treatment	Day 1 (± 3 days)	Day 14 (± 7 days)	Day 21 (± 3 days)	Day 38 (± 4 days)	Day 42 (± 3 days)	2-4 weeks after Cycle 3	10 days ± 5 days after surgery (or < 30 days after last treatment)
Chemistry l	x j	x k		x		x		x
Pregnancy test m	x j							
Coagulation (INR, aPTT)	x j							
TSH n	x j							x
Urinalysis o	x j							
CT or MRI of primary site (if present) and regional lymphatics	x p				x p (prior to cycle 3)			
Chest CT with contrast or PET scan	x p							
Blood sample for exploratory biomarker research q	x		x				x	
Tumor response assessments s	x r	x s		x		x	x	
Concomitant medications t	x	x		x		x		x
Adverse events u	x u	x u		x u		x u		x u
Atezolizumab administration v		x		x		x		
Surgical resection							SOC	
Adjuvant Therapy w								SOC

	Screening a	Treatment Cycles (21-day cycles)					Surgery	Follow-Up (or Treatment Discontinuation b )
		Cycle 1		Cycle 2		Cycle 3		

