	Within 28 days prior to start of treatment	Day 1 ( $\pm$ 3 days)	Day 14 ( $\pm$ 7 days)	Day 21 ( $\pm$ 3 days)	Day 38 ( $\pm$ 4 days)	Day 42 ( $\pm$ 3 days)	2-4 weeks after Cycle 3	10 days $\pm$ 5 days after surgery (or < 30 days after last treatment)

ADA=anti-drug antibody; HBcAb=hepatitis B core antibody; HBsAb=hepatitis B surface antibody; HBsAg=hepatitis B surface antigen; NA=not applicable; PK=pharmacokinetic; T3=triiodothyronine; T4=thyroxine; TSH=thyroid-stimulating hormone; WES=whole exome sequencing; WGS=whole genome sequencing.

Notes: On treatment days, all assessments should be performed prior to dosing, unless otherwise specified.

Assessments shaded in gray should be performed as scheduled, but the associated data do not need to be recorded in the patient's medical records (except in the case of an adverse event).

- a Results of standard-of-care tests or examinations performed prior to obtaining informed consent and within 28 days prior to start of treatment may be used; such tests do not need to be repeated for screening.
- b Patients who discontinue study treatment will return to the clinic for a treatment discontinuation visit not more than 30 days after the last dose of study treatment. The visit at which response assessment shows progressive disease may be used as the treatment discontinuation visit.
- c Informed consent must be documented before any study-specific screening procedure is performed, and may be obtained more than 28 days before initiation of study treatment.
- d If archival tissue is unavailable or is determined to be unsuitable for required testing, a pretreatment tumor biopsy is required. A pretreatment tumor biopsy will also be performed, when clinically feasible, for biomarker assessment. Refer to Section 4.6 or tissue sample requirements.
- e Includes respiratory rate, pulse rate, and systolic and diastolic blood pressure, and temperature. Record abnormalities observed at baseline in the patient's medical records. At subsequent visits, record new or worsened clinically significant abnormalities in the patient's medical records. For the first and subsequent infusions, vital signs should be measured prior to the infusion (taken same day during clinic visit or in infusion area) and, if clinically indicated, during or after the infusion.

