- f Record abnormalities observed at baseline in the patient's medical records. At subsequent visits, record new or worsened clinically significant abnormalities in the patient's medical records.
- g Perform a limited, symptom-directed examination at specified timepoints and as clinically indicated at other timepoints. Record new or worsened clinically significant abnormalities in the patient's medical records.

---

- h ECG recordings will be obtained during screening and as clinically indicated at other timepoints.
- i Hematology includes WBC count, hemoglobin, hematocrit, platelet count, differential count.
- j Screening laboratory test results must be obtained within 28 days prior to initiation of study treatment.
- k If screening laboratory assessments were performed within 96 hours prior to Day 1 of Cycle 1, they do not have to be repeated.
- l Chemistry panel (serum or plasma) includes sodium, potassium, chloride, bicarbonate, glucose, BUN or urea, creatinine, total protein, albumin, calcium, total bilirubin, alkaline phosphatase, ALT, AST.
- m All women of childbearing potential will have a serum pregnancy test at screening, within 28 days prior to initiation of study treatment.
- n Past TSH lab value may be used for screening if collected within 6 weeks prior to the first administration of atezolizumab.
- o Urinalysis includes pH, specific gravity, glucose, protein, ketones, and blood
- p Baseline imaging with CT or MRI of primary site (if present) and regional lymphatics; CT Chest or PET scan will be performed only if scans were not previously performed within 28 days of screening assessment. The same radiographic modality used to assess disease sites at screening should be used for subsequent tumor assessment at baseline and after cycle 2. **RECIST measurements are only required at baseline, after cycle 2, and ORR can be assessed after cycle 2/surgery.**
- q See Section 4.6 for details on exploratory research
- r All measurable and evaluable lesions should be assessed and documented at screening. Tumor assessments performed as standard of care prior to obtaining informed consent and within 28 days prior to initiation of study treatment do not have to be repeated at screening.

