## APPENDICES

### APPENDIX A: Participant Eligibility Checklist

#### I. Subject Eligibility Checklist

A Participant Eligibility Checklist must be completed in its entirety for each subject prior to registration. The completed, signed, and dated checklist must be retained in the patient's study file and the study's Regulatory Binder.

The study coordinator, treating physician and an independent reviewer must verify that the participant's eligibility is accurate, complete, and legible in source records. A description of the eligibility verification process should be included in the EPIC or other Electronic Medical Record progress note.

Protocol Title:	NEOADJUVANT ATEZOLIZUMAB IN SURGICALLY RESECTABLE ADVANCED CUTANEOUS SQUAMOUS CELL CARCINOMA
Protocol Number:	ENT0082 / IRB-59070
Principal Investigator:	[name]

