## Inclusion/Exclusion Criteria

Exclusion Criteria (From IRB approved protocol)	Yes	No	Supporting Documentation*
• Women of childbearing potential must have a negative serum pregnancy test result within 14 days prior to initiation of study treatment.			

\*All subject files must include supporting documentation to confirm subject eligibility. The method of confirmation can include, but is not limited to, laboratory test results, radiology test results, subject self-reporting, and medical record review.

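### Study calendar footnote m allows a serum pregnancy test up to 28 days before first dose, but exclusion 21 requires one within 14 days

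*Combined protocol and SAP*

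**What the plan says.** The pregnancy-test row of the study calendar (Section 9) has a single mark, in the screening column. Footnote m, attached to that row, gives the test its own window: "All women of childbearing potential will have a serum pregnancy test at screening, within 28 days prior to initiation of study treatment".

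Three general statements in the calendar also use 28 days:

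- The screening column is headed "Within 28 days prior to start of treatment".
- Footnote j, attached to the mark in this row, says "Screening laboratory test results must be obtained within 28 days prior to initiation of study treatment".
- Footnote a, attached to the screening column, says that results obtained "within 28 days prior to start of treatment may be used; such tests do not need to be repeated for screening". It covers only standard-of-care tests or examinations done before informed consent.

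The bullet under exclusion criterion 21 in Appendix A sets a shorter window: "Women of childbearing potential must have a negative serum pregnancy test result within 14 days prior to initiation of study treatment".

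Section 3.2 lists no exclusion criteria of its own. It says only "Refer to Participant Eligibility Checklist in Appendix A". Section 4.1 adds "All screening evaluations must be completed and reviewed to confirm that patients meet all eligibility criteria before enrollment".

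**The concern.** Footnote m and exclusion 21 concern the same test (serum), the same women and the same reference date (initiation of study treatment). Only the number of days differs. Section 4 makes the Section 9 calendar the schedule of activities for every patient, so it is the text that staff are likely to work from when booking tests.

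Someone following the calendar could accept a test that the eligibility criterion does not. If the checklist review catches this, the cost is a late repeat test and perhaps a delayed first dose. If it does not, a woman receives atezolizumab on a pregnancy test older than the protocol allows, and an ineligible patient has been treated. The protocol treats pregnancy as serious: it requires permanent discontinuation (Section 4.8), expedited reporting to the manufacturer (Section 7.5.2.6), and contraception or abstinence for 5 months after the last dose (inclusion 10).

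**Working it through.** The plan gives no computed figure to reproduce. The check is a comparison of the windows in the current text, all counted back from the start of study treatment.

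| Source | Scope | Accepted age of test |
|---|---|---|
| Calendar, footnote m | pregnancy test only | 0–28 days |
| Calendar, screening column heading | all screening items | 0–28 days |
| Calendar, footnote j | screening laboratory tests | 0–28 days |
| Calendar, footnote a | standard-of-care tests before consent | 0–28 days, no repeat needed |
| Appendix A, exclusion 21 | pregnancy test only | 0–14 days |

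**Step 1: overlap.** A test aged 0–14 days satisfies every row. The shorter window lies wholly inside the longer one.

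**Step 2: difference.** A test aged 15–28 days satisfies footnote m and fails exclusion 21. That is 28 − 14 = 14 day-values. No test age satisfies exclusion 21 and fails the calendar.

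**Step 3: does anything else in the calendar close the gap?** No. There is no pregnancy test on Cycle 1 Day 1 or at any later visit. Footnote k, which has a 96-hour rule for laboratory work before Cycle 1 Day 1, is attached only to hematology and chemistry.

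**Step 4: does anything support 28 days for this test?** Inclusion 7 has a 28-day laboratory window, but it names AST, ALT, total bilirubin, alkaline phosphatase and TSH. It does not mention a pregnancy test.

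**Step 5: which window applies?** The documents contain no precedence clause. Section 3.2 places the exclusion criteria in Appendix A, and Section 4.1 requires all criteria to be met before enrollment. The reasonable reading is that 14 days decides eligibility. It is also the safer reading.

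Both windows stand in the operative text of version 15, so the difference is not between current text and the amendment log.

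**The case against.** The case for leaving this alone is fair in several respects.

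- **The windows are nested.** Staff can comply with both texts by testing within 14 days. This stands and limits the severity.
- **Safeguards exist.** Eligibility is confirmed before enrollment, and Appendix A says "The study coordinator, treating physician and an independent reviewer must verify" that the eligibility record is accurate and complete. Each subject file must also hold supporting documentation, and inclusion 10 requires abstinence or highly effective contraception. This also stands, but does not remove the problem. The checklist is completed before registration, while the 14-day window runs to the first dose. As an illustration, assume a test 10 days old at registration and a first dose 8 days later. The test is then 10 + 8 = 18 days old at dosing, the checklist is already signed, and the calendar still accepts the test. The documents do not say how long that interval usually is.
- **Only footnote m is specific to this test.** A reader might count four calendar statements as four separate contradictions of exclusion 21. The documents do not support that: the column heading and footnotes a and j are general screening windows, which a corrected footnote m can override.
- **Footnote a is narrow.** A reader might infer that it excuses any test 15–28 days old from repetition. It does not. It applies only to standard-of-care tests performed before consent, so a test drawn for the study after consent is outside it.

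A reader might also infer that women will be dosed on out-of-window tests, or that the trial's conclusions are at risk. Neither follows. The documents give no number of women of childbearing potential from which to estimate a deviation rate, and no statistical quantity depends on this window.

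**Conclusion.** The inconsistency is real, minor and worth correcting. The calendar's specific instruction for the pregnancy test is 14 days longer than the eligibility criterion, and nothing else in the calendar reconciles the two.

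The conclusion rests on one inference: that Appendix A decides eligibility because Section 3.2 refers to it, although no clause ranks it above the calendar. If the sponsor meant 28 days, the texts would still disagree and one would still need editing. Nothing in the documents argues for relaxing the 14-day rule, and that rule is not challenged here.

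The 20-patient sample size and its power, the rule of 17 or more successes, and the definition of evaluable patients are all unchanged.

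**What to change.** In footnote m, replace 28 days with 14 days, remove the reference to screening as the time of the test, and add: *The 28-day windows in the screening column heading and footnotes a and j do not apply to this test.* Leave exclusion 21 unchanged.

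That one footnote resolves the row. Removing superscript j from the pregnancy-test mark and adding an exception to footnote a are optional tidying.

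The cost is one footnote edit in the next amendment. In operation it may mean an occasional repeat serum test, which exclusion 21 already demands.

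If the footnotes are being edited anyway, footnote n could be shortened too. It accepts a TSH up to 6 weeks (42 days) old, whereas inclusion 7 and footnote j, which is also attached to the TSH screening mark, both say 28 days. Shortening footnote n to 28 days matches both. Adding a 6-week allowance to inclusion 7 would leave footnote j in conflict. This is a separate housekeeping item and the main point does not depend on it.

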#### **4.5 Tumor and Response Evaluations**

Patients will undergo tumor assessments at baseline and according to the schedule specified in the study calendar (section 9). These are clinical observations and judgements used by the investigator and medical team of the patient's clinical status to determine the appropriateness of continuing study intervention. At the investigator's discretion, tumor assessments may be repeated at any time if progressive disease is suspected. All tumor assessments following surgical resection will be per standards of care.

All measurable and evaluable lesions should be assessed and documented at screening. Tumor assessments performed as standard of care prior to obtaining informed consent and within 28 days prior to initiation of study treatment do not have to be repeated at screening.

Overall response at a single timepoint will be assessed by the investigator using RECIST v1.1 (see Appendix F) at baseline and Day 38 ( $\pm 4$  days).

Screening assessments must include CT scans (with IV contrast) or MRI scans of the primary site (if present), regional lymphatics, thorax, and depending on the location of the tumor, may include other relevant anatomy. PET/CT or CT of the thorax are appropriate preoperative workup; however, cannot substitute for either the CT or MRI of the primary site if present, and regional lymphatics. CT of the thorax need not be repeated after baseline unless there is clinical indication. If a CT scan with contrast is contraindicated (e.g., in patients with impaired renal clearance), a non-contrast CT scan of the chest may be performed and MRI scans of regional lymphatics and, if applicable, primary site should be performed. The same radiographic procedures used to assess disease sites at screening should be used for subsequent tumor assessments (e.g., the same contrast protocol for CT scans) as listed in section 9. At the investigator's discretion, other methods of assessment of measurable disease as per RECIST v1.1 may be used.

If a CT scan for primary tumor assessment is performed in a positron emission tomography (PET)/CT scanner, all efforts should be made so the CT acquisition is consistent with the standards for a full-contrast diagnostic CT scan.

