### **METHODS FOR ASSESSING LESIONS**

All measurements should be recorded in metric notation, using calipers if clinically assessed. All baseline evaluations should be performed as close as possible to the treatment start and never more than 4 weeks before the beginning of the treatment.

The same method of assessment and the same technique should be used to characterize each identified and reported lesion at baseline and during the study. Imaging-based evaluation should always be the preferred option.

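### Study Calendar footnote p counts the 28-day scan-reuse window from screening, which would permit a RECIST baseline up to 56 days before first dose and contradicts the 28-day limit before treatment stated elsewhere in the protocol

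*Combined protocol and SAP*

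**What the plan says.** Footnote p is attached to both imaging rows of the Study Calendar (CT or MRI of the primary site and regional lymphatics; chest CT or PET). It calls for baseline imaging "only if scans were not previously performed within 28 days of screening assessment". The anchor is the screening assessment. The screening column is headed "Within 28 days prior to start of treatment".

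Four other provisions use the start of treatment as the anchor:

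- Section 4.5: standard-of-care tumor assessments made before consent and "within 28 days prior to initiation of study treatment do not have to be repeated at screening".
- Footnote r, on the tumor response row of the screening column, repeats that rule.
- Footnote a, on the screening column as a whole: standard-of-care results "within 28 days prior to start of treatment may be used".
- Appendix F, on methods for assessing lesions: baseline evaluations are to be "performed as close as possible to the treatment start and never more than 4 weeks before the beginning of the treatment".

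RECIST measurements are required only at baseline and after cycle 2 (footnotes p and s; Section 4.5 gives Day 38 ± 4).

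**The concern.** With one required on-treatment RECIST scan, each patient's response rests on two measurements, and the age of the first one matters. Any growth between the baseline scan and dose 1 is credited to the treatment period. It makes true shrinkage look smaller, which lowers the objective response rate, and it uses up part of the 20% margin before progression is declared.

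The eligibility criteria do not close the gap. Inclusion criterion 4 accepts measurable disease without protocol-specified imaging, so an old scan would not be caught there. Section 12.6 uses RECIST to assess progression. Progression during neoadjuvant treatment is a failure on the primary outcome (Sections 1.1 and 10.1), and four failures stop the study (Sections 7.2 and 12.3). A measurement artefact could therefore reach the main decision, although that step depends on how progression is judged.

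**Working it through.** The plan states no figure for the age of the baseline scan or for tumor growth, so there is no plan figure to reproduce. The inputs from the documents are the windows and the RECIST thresholds.

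**Inputs**

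- Scan-reuse window: 28 days before screening (footnote p).
- Screening window: 28 days before first dose (screening column, Section 9).
- Limit elsewhere: 28 days or 4 weeks before treatment (Section 4.5, footnotes a and r, Appendix F).
- On-treatment scan: Day 38 (Section 4.5).
- Partial response: at least a 30% decrease from baseline. Progression: at least a 20% increase over the smallest sum on study, baseline included, and at least 5 mm in absolute terms (Appendix F).
- Assumption, not in the documents: diameters grow by g = 1% or 3% per week between the baseline scan and dose 1.

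**Step 1: scan age.** Under footnote p alone, 28 + 28 = 56 days before dose 1. Under the other provisions, 28 days. The interval from baseline to the Day 38 scan is 56 + 37 = 93 days against 28 + 37 = 65 days.

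**Step 2: growth before dose 1.** G = (1 + g)^w, with w = 4 weeks for a 28-day-old scan and w = 8 weeks for a 56-day-old scan.

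**Step 3: how a true 30% shrinkage from dose 1 reads.** 0.70 × G − 1.

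**Step 4: change from dose 1 that reaches the 20% progression threshold.** 1.20 / G − 1.

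| g per week | Scan age | G | True −30% reads as | Change from dose 1 that reaches +20% |
|---|---|---|---|---|
| 1% | 28 days | 1.041 | −27% | +15% |
| 1% | 56 days | 1.083 | −24% | +11% |
| 3% | 28 days | 1.126 | −21% | +6.6% |
| 3% | 56 days | 1.267 | −11% | −5% |

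Only the difference between the 28-day and 56-day rows at the same growth rate is due to footnote p. The 28-day rows show what the plan accepts in any case.

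**Step 5: the absolute criterion.** A 20% increase equals 5 mm when the baseline sum is 5 / 0.20 = 25 mm. Below 25 mm, more than a 20% increase is needed, so the last column applies to sums of 25 mm or more.

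**Cross-check in volume terms.** A 20% larger diameter is 1.2³ = 1.728 times the volume, or 0.789 doublings. Growth before treatment alone reaches 20% if the volume doubling time is at most 56 / 0.789 ≈ 71 days with a 56-day-old scan, or at most 28 / 0.789 ≈ 35 days with a 28-day-old scan. The documents do not say where these tumors lie on that scale.

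**The case against.** The strongest reply is that the plan read as a whole already forbids a 56-day baseline. The screening column heading, footnote a on that same column, footnote r, Section 4.5 and Appendix F all point to the start of treatment, and footnote p is the odd one out. This stands as far as the plan's evident intent goes. It does not remove the conflict: footnote p is the note on the imaging rows, it is worded as a waiver of the scan, and it is the same note that sets the RECIST timepoints. No text says which provision prevails.

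Second, the semicolon in footnote p might confine the waiver to chest imaging. But the note marks both imaging rows, and on that reading its first clause has no verb.

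Third, the calendar has a tumor assessment on Cycle 1 Day 1, and Section 12.6 records the greatest dimension of visible lesions at each cycle. For visible lesions this could expose growth before dose 1. It does not help for nodal or other non-visible disease, and that measurement is not designated as the RECIST baseline.

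Fourth, the growth rates are assumed. That is correct. They show the direction and a range, not an estimate.

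A reader might go further and infer that growth before treatment will be counted as progression, and so as primary failures toward the four-failure stop. The documents do not support that. RECIST progression also needs the 5 mm increase. Sections 1.1 and 10.1 speak of disease progression without equating it to RECIST progression, Section 2.4 refers to clinical or radiographic evidence, and Section 4.8 rests loss of clinical benefit on an integrated assessment by the investigator.

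**Conclusion.** The inconsistency is real and is wrong as written. Footnote p permits a baseline scan up to 56 days before first dose, twice the limit the protocol sets in four other places. If a site applies it, the objective response rate can be biased downward and RECIST progression can be inflated.

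Under the assumed growth rates, the additional 28 days take the reading of a true 30% shrinkage from 27% to 24% (1% per week) or from 21% to 11% (3% per week). The change from dose 1 that reaches the progression threshold falls from +15% to +11%, or from +6.6% to −5%. At the higher rate, a patient whose tumor has shrunk by about 5% since dose 1 would sit at the threshold, provided the 5 mm criterion is also met.

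These figures rest on the assumed growth and on a scan at the extreme of the window. The documents do not show how many patients would have such a scan. An effect on the primary endpoint or the stopping rule may follow but need not.

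**What to change.** Reconcile footnote p with Section 4.5, footnotes a and r, and Appendix F so that one anchor governs the RECIST baseline scan: the start of treatment, which those provisions already use.

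A text change cannot help patients already scanned. When the objective response rate and RECIST progression are reported, flag any enrolled patient whose baseline scan was more than 28 days before dose 1, so that the reader can see whether the result depends on them.

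The cost is one footnote and one flag derived from two dates. A few patients with older outside scans may need a repeat, a burden that Section 4.5 and Appendix F already imply.
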